13.6.1.3 Reporting of serious adverse events

Investigators and other site personnel must inform appropriate AstraZeneca representatives of any SAE that occurs in the course of the study within 1 day (ie, immediately but no later than the end of the next business day) of when he or she becomes aware of it.

The AstraZeneca representative will work with the investigator to compile all the necessary information and ensure that the appropriate AstraZeneca Drug Safety Department receives a report by day 1 for all fatal and life-threatening cases and by day 5 for all other SAEs.

Follow-up information on SAEs must also be reported by the investigator within the same time frames.

If a non-serious AE becomes serious, this and other relevant follow-up information must also be provided to AstraZeneca within 1 day as described above. For a non-serious AE that becomes serious but which is not fatal or life-threatening a report should be received within 5 days.

All SAEs have to be reported, whether or not considered causally related to the investigational product or to the study procedure(s). All SAEs will be recorded in the case report form. The investigator and/or Sponsor are responsible for informing the Ethics Committee and/or the Regulatory Authority of the SAE as per local requirements.

14. PART B - STUDY MANAGEMENT

14.1 Monitoring

14.1.1 Study monitoring

The monitoring of this study will be performed in accordance with the principles of Good Clinical Practice (GCP) as laid out in the International Conference on Harmonisation (ICH) document "Good Clinical Practice: Consolidated Guideline".

14.1.2 Data verification

It is a prerequisite of this study that the study monitor has direct access to source data for data verification. This will be done by comparing data from the CRFs with those in the patient's medical notes (permission from the patient will be sought as part of the consent process). Such verification is an essential element of quality control, as it allows the rectification of transcription errors and omissions.

Data for which the CRF will be regarded as source data will be described in a separate document.

Monitoring including source data verification should routinely be performed prior to the transfer of data to Data Management. However, data will not necessarily be monitored prior to Safety Review Committee meetings.

14.2 Audits and inspections

Authorised representatives of AstraZeneca, a regulatory authority, an Ethics Committee may visit the centre to perform audits or inspections, including source data verification. The purpose of an AstraZeneca audit or inspection is to systematically and independently examine all study-related activities and documents to determine whether these activities were conducted, and data were recorded, analysed, and accurately reported according to the protocol, GCP guidelines of the ICH and any applicable regulatory requirements. The investigator should contact AstraZeneca immediately if contacted by a regulatory agency about an inspection at his or her centre.

14.3 Training of staff

The principal investigator will maintain a record of all individuals involved in the study (medical, nursing and other staff). He will ensure that appropriate training relevant to the study is given to all of these staff, and that any new information of relevance to the performance of this study is forwarded to the staff involved.

14.4 Changes to the protocol

Study procedures will not be changed without the mutual agreement of the principal investigator and AstraZeneca.

If it is necessary for the study protocol to be amended, the amendment and/or a new version of the study protocol must be notified to or approved by the Ethics Committee, and also the local regulatory authority, before implementation. Local requirements must be followed.

If a protocol amendment requires a change to a the Informed Consent Form, then the Ethics Committee must be notified. Approval of the revised Informed Consent Form by the Ethics Committee is required before the revised form is used.

AstraZeneca will distribute amendments and new versions of the protocol to the principal investigator(s) who in turn is responsible for the distribution of these documents to his or her Ethics Committee and to the staff at his or her centre. The distribution of these documents to the regulatory authority will be handled Regulatory Affairs at AstraZeneca.

86(95)

14.5 Study agreements

The principal investigator at each centre must comply with all the terms, conditions and obligations of the study agreement for this study. In the event of any inconsistency between this protocol and the study agreement, this protocol shall prevail.

14.6 Study timetable and end of study

Part B of the study is expected to start in November 2007 (see Section 12.1) and to be completed by April 2008

End of study is defined as database lock, which is the time point after which no patient will be exposed to study related activities.

14.7 Data management

Data entry, editing, clean file and analysis will be performed by AstraZeneca R&D Lund, Sweden.

Medical and surgical history and AEs will be coded using the standardised dictionary MedDRA. Medications will be coded using the AZ approved Drug Dictionary (AZDD) including ATC and route of administration will be coded using Committee for Medicinal Products for Human Use (CHMP) dictionary.

Clean file will be declared after a final quality check has been performed on a sample of the data. Before declaring Clean File, the possible influence of protocol deviations on the statistical analysis will be discussed.

Results from the PK assessments will be electronically transferred into the study database at the time of Clean File. After the database is locked, all data will be transferred to the statistician at AstraZeneca R&D Lund, Sweden, for statistical analysis. After locking the database, editing in the database will not be allowed without proper documentation.

Procedures for verification and validation of data will be described in a separate document.

14.7.1 Case report forms

Paper CRFs (pCRFs) will be used to record all data not captured electronically. Data should be recorded legibly onto the pCRFs in blue or black ballpoint pen. Correction fluid or covering labels must not be used.

The AstraZeneca Monitor will check data at the monitoring visits to the study site. The Investigator will ensure that the data in the pCRFs are accurate, complete and legible.

Approved

87(95)

Data from the completed pCRFs will be entered onto AstraZeneca's clinical study database and validated. Procedures for verification and validation of data will be described in the Data Management Plan. Any missing, impossible or inconsistent recordings in the pCRFs will be referred back to the Investigator using a data query form (DQF), and be documented for each individual patient before clean file status is declared.

14.7.2 Electronic data capture (Immediate data entry) Not applicable in Part B

14.7.3 Electronic data capture at bedside

During the treatment visits all data, except for medication, AEs, lung function, 12-lead ECG, laboratory results and tremor/palpitations scoring will be captured electronically at bedside.

The Investigator will ensure that the captured data are correct before transferred to the AstraZeneca Clinical Study Database for final checking. Any changes made during validation will be documented with a full audit trail within the Electronic Data Capture application.

Any missing, impossible or inconsistent entries discovered after the data have been transferred to the clinical study database will be referred back to the Investigator using data query forms, and be documented for each individual patient before clean file status is declared.

PART B - PHARMACOKINETIC, PHARMACODYNAMIC, 15. SAFETY AND STATISTICAL METHODOLOGY

15.1 Pharmacokinetic / pharmacodynamic evaluation

15.1.1 Calculation or derivation of pharmacokinetic variables

The pharmacokinetic analyses will be performed by the Department of Clinical Information Science, AstraZeneca R&D Lund, Sweden.

From the plasma concentrations of AZD3199 collected following a single dose, pharmacokinetic parameters will be calculated using standard non-parametrical methods. The pharmacokinetic parameters will include: the maximum plasma drug concentration (C_{max}) , the time to maximum plasma drug concentration (t_{max}) , the area under the (plasma drug concentration-time) curve from time zero to infinity (AUC), terminal half-life of drug in plasma ($t_{1/2}$), apparent plasma clearance (CL/F).

15.1.2 **Calculation or derivation of pharmacodynamic variables**

Pharmacodynamic variables in this study will include potassium and lactate concentrations, blood pressure, heart rate, QTcB, tremor, palpitations and FEV₁. For each variable the maximum effect during the post-dose measurement interval (the minimum value, Emin, for

Approved by

potassium and diastolic blood pressure, and the maximum value, E_{max} , for other variables) and the average effect, E_{av} (AUC/length of interval), will be computed and used as variables of systemic and local effects. In addition, for FEV₁, the effect during 22 - 26 hours post-dose, E_{22-26} , will be calculated. Further, data collected at each assessment time will be used in the statistical evaluation to follow the duration of effect of the drug.

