Single ascending doses will be administered as a solution for nebulisation for inhalation via Spira nebuliser.

Planned doses for Part A:

A PRINTED COPY OF AN ELECTRONIC DOCUMENT. PLEASE CHECK ITS VALIDITY BEFORE USE

5 H

THIS

Table S1	Planned lung deposited doses							
Dose level	1	2	3	4	5	6	7	8
Lung deposited dose (µg)	2	10	40	160	640	1500	3000	4500

Doses are expressed as AZD3199 free base

These doses may be adjusted during the course of the study, after evaluation of Safety Review Committee, depending on safety, pharmacodynamic and pharmacokinetic results obtained. Pre-study calculations of inhaled aerosol disposition will be considered when deciding the actual dose delivered to healthy subjects.

Planned doses for Part B: Part B will comprise a maximum of 4 dose levels and will employ 2 cohorts of 8 patients. These cohorts will be administered one placebo dose, one low and one high dose each. The starting dose will not exceed half the dose showing systemic pharmacological activity in the healthy subjects. If no systemic pharmacological effects are seen after Dose 5 in Part A, Part B in patients will be initiated with a starting dose of at most half of Dose 5.

Duration of treatment

Part A: A single dose will be administered to each subject.

Part B: One placebo dose and 2 single doses (a lower and a higher dose) of AZD3199 will be administered to each patient with a wash-out of at least 1 week in between the active doses.

Variables

- Pharmacokinetic

Standard pharmacokinetic parameters calculated from AZD3199 concentrations in plasma and urine (urine, Part A only).

- Pharmacodynamic

FEV₁ (Part B only), potassium and lactate concentrations, tremor and palpitations, heart rate, QTcB (Part B only), and blood pressure

- Safety

Incidence and nature of AEs, effects on ECG parameters, blood pressure (BP), pulse, lung function, body temperature (Part A only) and laboratory variables (clinical chemistry, haematology and urinalysis)

- Statistical methods

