ERS	European Respiratory Society
FEV ₁	Forced expiratory volume during 1 second
GAME	Global Arrhythmia Monitoring and ECG; system for secure and compliant dECG data transfer from AZ CPUs to the central server.
GCP	Good Clinical Practice

Abbreviation or special term	Explanation
HPLC/MS/MS	High Performance Liquid Chromatography/Tandem Mass Spectrometry
ICH	International Conference on Harmonisation
IEC	Independent Ethics Committee
IPS	Investigational Products
IRB	Institutional Review Board
LABA	Long-acting β_2 -agonist
LEFTS	Local ECG Files Transfer and Storage; the AZ CPU local dECG repository
MABEL	Minimal Anticipated Biological Effect level
OAE	Other Significant Adverse Event (ie, adverse events of particular clinical importance, other than SAEs and those AEs leading to discontinuation of the subject from study treatment; see definition in Section 4.6.1.1).
pCRF	paper Case Report Form
PGx	Pharmacogenetics
РК	Pharmacokinetics
PR (PQ)	ECG interval measured from the beginning of the P wave to the beginning of the Q wave or beginning of R wave in the absence of a Q wave. PR (PQ) represents the time interval from start of atrial depolarisation to the start of ventricular depolarisation.
Principal investigator	A person responsible for the conduct of a clinical study at a study site. Every study centre has a principal investigator.
QRS	ECG interval measured from the beginning of the Q wave (or the R wave if Q is missing) to the J point; the time interval of ventricular depolarisation.
QT	ECG interval measured from the beginning of the Q wave (or the R wave if Q is missing) to the end of the T wave; the time interval of ventricular activation and recovery
QTcB	QT interval corrected for heart rate using Bazett formula.
QTcF	QT interval corrected for heart rate using Fredericia formula.

15(95)

Abbreviation or special term	Explanation								
QTcX	QT interval corrected for heart rate using a specific individualised factor.								
QT _{tang}	QT interval measured by EClysis from the beginning of the Q wave or the R wave if Q is missing, to the intercept between the isoelectric line and the regression line, derived on the T-wave downstroke from values between 80 and 20 % of the T-top amplitude.								
RR interval	The time between corresponding points on 2 consecutive R waves on ECG; the interval from one ventricular depolarisation to the next. In EClysis, the variable is named RR before.								
SAE	Serious adverse event								
SRC	Safety Review Committee								

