2.2 Secondary objective(s)

The secondary objectives of Part A of the study are:

- 1. to investigate the pharmacokinetics (PK) of single ascending doses of AZD3199 by assessment of drug concentration in plasma and urine and calculated PK parameters, with particular attention to dose linearity
- 2. to investigate extrapulmonary β_2 adrenoreceptor mediated effects of single ascending doses of AZD3199 by assessment of potassium and lactate concentrations, tremor and palpitations, heart rate, QTc, and blood pressure
- 3. to obtain material for possible exploratory analysis of metabolites of AZD3199 in urine and plasma (exploratory objective)

An optional objective in this study is to collect pharmacogenetic samples for possible retrospective exploratory analysis, investigating the influence of genotype on pharmacokinetics (and pharmacodynamic response where appropriate). This genetic part is described in detail in Appendix D.

18(95)

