6.1.2 Calculation or derivation of pharmacodynamic variables

Pharmacodynamic variables in this study will include potassium and lactate concentrations, blood pressure, heart rate, tremor and palpitations. For each variable the maximum effect during the post-dose measurement interval (the minimum value, E_{min} , for potassium and diastolic blood pressure, and the maximum value, E_{max} , for other variables) and the average effect, E_{av} (AUC/length of interval), will be computed and used as variables of systemic and local effects.

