12.1.1 Stopping criteria for dose escalation

A Safety Review Committee (see Section 15.6) will review safety and tolerability results after each dose before proceeding to the next dose.

Any safety concerns will be evaluated using the following guidance, which is based on preclinical studies with AZD3199 and knowledge from clinical experience with LABAs. The guidance will be used to decide if a patient can be re-exposed with AZD3199 at a higher dose.

Stopping guidance for dose escalation

- Cardiovascular system
 - A QTcF > 500 ms (QT interval corrected for heart rate by Fredericia method) or a QTcF prolongation > 60 ms on average compared to baseline sustained for more than 30 minutes, or on 2 contiguous time points.
 - A persistent (>60 min) heart rate >120 beats/min related to the study drug according to the Investigator
 - A clinically significant supraventricular or ventricular tachyarrhythmia of any kind, except isolated ventricular extrasystoles according to the Investigator
 - A persistent (>30 min) diastolic blood pressure <45 mm Hg related to the study drug according to the Investigator

Potassium concentrations

A persistent (>30 min) plasma potassium concentration <2.8 mmol/L

Liver

Increase in AST or ALT≥ 3 x upper limit of normal reference interval (ULN) or bilirubin >2 x ULN or an increase in bilirubin ≥1.5 x ULN and AST or ALT> 2 x ULN.

Any other clinically relevant changes and significant changes in the safety parameters (e.g. ECG parameters, blood pressure, pulse, spirometry, body temperature, laboratory assessments and AEs) making the continuation of dosing unjustified.

Dose escalation will be stopped if the mean total plasma AUC or C_{max} of AZD3199 is higher than 111 nmol/L*h or 63.0 nmol/L, respectively. (Section 12.2.1)

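### Part B names Bazett QTcB as its only pharmacodynamic QTc variable although heart rate is expected to rise and every QTc limit uses QTcF; Part A's derived pharmacodynamic list omits QTc

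*Protocol*

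**What the plan says.** **Part B.** Section 15.1.2 names QTcB among the pharmacodynamic variables ("blood pressure, heart rate, QTcB, tremor, palpitations"). The synopsis, under Variables, has "heart rate, QTcB (Part B only), and blood pressure". The abbreviation list defines QTcB as the "QT interval corrected for heart rate using Bazett formula". Section 15.1.2 derives a post-dose maximum (E_max) and a time-averaged value (E_av) for each variable and also uses the data at each assessment time. Section 15.3.4 puts the pharmacodynamic parameters into analysis of variance, active against placebo and dose against dose.

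**Limits.** The stopping guidance in section 12.1.1 reads "A QTcF > 500 ms (QT interval corrected for heart rate by Fredericia method) or a QTcF prolongation > 60 ms on average". Section 3.1.1 has the same rule for Part A and section 12.3.5.1 has it for discontinuation in Part B. The exclusion criteria in 3.3.3 and 12.3.3 also use QTcF.

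**Part A.** Secondary objective 2 (section 2.2) covers "tremor and palpitations, heart rate, QTc, and blood pressure". The derived pharmacodynamic list in section 6.1.2 ends with "blood pressure, heart rate, tremor and palpitations" and contains no QTc. Section 6.2 keeps QTc among the ECG safety variables without naming a correction; section 15.2.1 does the same for Part B. Sections 3.2.1 and 4.4.2.1 provide a dummy day in the last two dose groups to obtain individual QT correction factors.

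**The concern.** Section 3.2.1 names a heart-rate increase as a marker of systemic activity. Section 12.2.2 reports both a heart-rate increase and QTc prolongation in the dog, so a real repolarisation effect is plausible and has to be told apart from a rate effect. Bazett's formula over-corrects as rate rises unless QT happens to follow the square root of RR. The artefact then points towards prolongation and grows with the heart-rate response, so it can look like a dose-response, which section 15.3.1 gives as the focus of the Part B evaluation. E_max adds to this because it tends to fall near peak rate.

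The protocol defines QTcB, QTcF and QTcX but gives no reason for analysing QTcB. As written, the answer to Part B secondary objective 3 on QTc is on a different scale from the limits applied to the same patients. In Part A, the randomised, double-blind part with digital ECGs, QTc misses the baseline-adjusted model altogether.

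**Working it through.** The protocol gives no QTc effect size, so there is no figure to reproduce. The check is how far each correction moves when only heart rate changes.

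**Inputs from the protocol.** The heart-rate step is 15 beats/min, the threshold for a systemic effect in sections 3.4.2.1 and 12.1. That threshold is defined on mean maximum resting pulse against placebo; using it as a step in ECG heart rate is an assumption. The upper case is 120 beats/min, the heart-rate level in section 12.1.1.

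**Assumptions not in the protocol.** Baseline QTcF is 400 ms, resting rate is 60 to 70 beats/min, and the QT-RR exponent b is 0.25, 1/3, 0.40 or 0.50.

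**Formulas.** RR = 60/HR; QTcB = QT/RR^(1/2); QTcF = QT/RR^(1/3). With no drug effect on repolarisation, QT1 = QT0 × (RR1/RR0)^b.

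**One case in full (60 to 75 beats/min, b = 1/3).** RR goes from 1.0 to 0.8. QT goes from 400 to 400 × 0.8^(1/3) = 371.3 ms. QTcB goes from 400 to 371.3/0.8944 = 415.2 ms, a change of +15.2 ms. QTcF stays at 400 ms.

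**Apparent change in ms for a 15 beats/min rise (from 60 / 65 / 70 beats/min):**

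| b | QTcB | QTcF |
|---|---|---|
| 0.25 | +22.9 / +21.6 / +20.4 | +7.5 / +7.0 / +6.5 |
| 1/3 | +15.2 / +14.3 / +13.5 | 0 / 0 / 0 |
| 0.40 | +9.0 / +8.5 / +8.0 | -5.9 / -5.5 / -5.1 |
| 0.50 | 0 / 0 / 0 | -14.6 / -13.6 / -12.7 |

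At 120 beats/min with b = 1/3, QTcB moves by +49.0 ms from 60 and +38.6 ms from 70 beats/min; QTcF moves by 0.

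**Reading the table.** QTcB errs upward at every exponent below 0.5. QTcF errs upward below 1/3 and downward above it. The proportional errors depend on b - 1/2 and b - 1/3, so they are equal in size at b = (1/2 + 1/3)/2 = 5/12, about 0.42. Below that QTcF has the smaller error; above it QTcB does.

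**Part A, sections side by side.** Section 2.2 lists QTc as an extrapulmonary effect and section 4.3.4 places it among the pharmacodynamic measurements. Section 6.1.2 omits it. Section 6.3.4 applies analysis of variance with baseline as covariate to the pharmacodynamic parameters, pooling placebo subjects across dose levels. QTc is not on the list that feeds that model.

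**The case against.** **No safety decision rests on QTcB.** This stands. Exclusion, escalation and discontinuation all use QTcF, and section 15.3.2 makes potassium E_min the primary measure of systemic side effects. QTcB serves one secondary objective, in cohorts of 8 set on feasibility (15.3.5).

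**Rate can be inspected.** A reader might infer that a true QT effect could not be separated from rate. The protocol does not support that. Heart rate is analysed alongside QTcB with the same summaries, section 13.4.2.1 records QT and heart rate from pre-dose to 12 h, and QTcF has to be derived for the limits anyway.

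**Part A does compare QTc with placebo.** A reader might infer from 6.1.2 that it does not. Section 6.2 says safety data, which include QTc, are compared with placebo at each dose level, and 6.3.4 pools the placebo subjects. What is missing is the derived variable and the model-based comparison, together with the name of the correction.

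**QTcF is not exact.** This also stands. Its zero change in the table holds by construction at b = 1/3, and above that it understates QT when rate rises. A rate increase therefore need not read as QTcB prolongation: the size depends on an exponent the protocol does not give.

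**Heart-rate effects may be small.** The Part B starting dose is capped at half the dose showing systemic activity, and 120 beats/min is a stopping level, not a typical response. But section 12.2.1 expects extrapulmonary effects at the high dose, so some rate increase there is anticipated.

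**Conclusion.** The point holds with moderate severity. Part B fixes, without a stated reason, a QTc variable that is biased towards false prolongation whenever the QT-RR exponent is below 0.5, for a drug expected to raise heart rate, and on a different scale from all the protocol's own QTc limits. For a 15 beats/min rise the artefact is about +8 to +23 ms for exponents from 0.40 down to 0.25 and vanishes at 0.50. These sizes rest on the assumed baseline QTcF of 400 ms, resting rate of 60 to 70 beats/min and exponents. The case for QTcF is agreement with the limits and a smaller error below an exponent of about 0.42; it is not that QTcF is free of error.

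The Part A point is narrower: objective 2 and section 6.1.2 do not match, so QTc is compared with placebo only as safety data, with no correction named. In both parts the harm is to the interpretation of a secondary objective, not to the protection of participants. This is not detail left to a statistical analysis plan, because the protocol itself names the Part B variable and lists the Part A ones.

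**What to change.** - **Section 15.1.2 and synopsis:** make QTcF the Part B pharmacodynamic QTc variable, with E_max, E_av and the time-point analysis already planned. Keep QTcB at most as supportive, shown beside heart rate.
- **Section 6.1.2:** add QTcF, so that it enters the baseline-adjusted comparison with pooled placebo in 6.3.4. For the two dose groups with a dummy day, add the individualised correction (QTcX). Bring the synopsis variable list into line.
- **Sections 6.2 and 15.2.1:** name the correction used in the QTc safety summaries.

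The cost is wording and slightly more analysis work. QT and heart rate are already recorded in both parts (sections 4.3.4, 5.7.4, 13.3.5 and 13.4.2.1), and QTcF is already needed for the limits, so no new measurement is required.
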